
Study Drug, Dose Schedule, and Mode of Administration:
	
REL-1017 consists of d-methadone hydrochloride (HCl) in a powder formulation. The following doses will be used in the study:
 
 • REL-1017 75 mg QD Day 1, 25 mg REL-1017 QD Day 2-7 • REL-1017 100 mg QD Day 1, 50 mg REL-1017 QD Day 2-7 • Placebo (Ocean Spray® Diet Cranberry Juice) 
REL-1017 will be provided as a powder and prepared as a solution with Ocean Spray® Diet Cranberry Juice on site to obtain a final volume of 100 mL for dosing.
 
Patients will continue to take the same, stabilized antidepressant medication that they were taking at Screening throughout the course of the study, and the supply of medication during the confined study period will be arranged and assured by the Investigator.
 
An unblinded pharmacist will assign study drug to patients according to randomized treatment codes provided by the Interactive Web Response System (IWRS). The randomization code used in the IWRS will be prepared by a statistician who is not working as a statistician on the study in any other capacity. The study drug solution or Placebo will be prepared within 3 hours of administration in blinded containers, and then will be dispensed to blinded study staff for administration to the patients.
 
After drinking the 100 mL of study drug, 25 mL of non-carbonated water will be added to the study drug container and gently swirled. The patient will drink this rinse volume followed by 125 mL of non-carbonated water to drink immediately thereafter.
 
All dosing must be completed within 5 minutes.
 
Dosing will take place once daily in the morning after an overnight fast of at least 8 hours.

Study Population and Duration of Participation
	
Adult patients with MDD who are diagnosed with a current major depressive episode (MDE) and who have experienced an inadequate response to 1 to 3 courses of treatment with an adequate dose and duration (as defined by the Antidepressant Treatment Response Questionnaire [ATRQ]) of an antidepressant medication for the current episode will be randomized to study drug in a 1:1:1 ratio.
 
Approximately 120 patients will be screened, and approximately 60 qualified patients will be randomized to study drug in a 1:1:1 ratio (approximately 20 patients per arm). Each patient will participate for up to 51 days (30 days Screening, 7 days treatment, and 14 days of observation and follow-up).

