3.2 Study Procedures

The overall duration of the study will be up to 51 days per patient. All patients will be admitted to the clinical research unit (CRU) for a period of approximately 10 days during which they will receive daily doses of REL-1017 or Placebo for 7 consecutive days. The Screening Visit will assess patient eligibility to participate in the study and will occur between Day -30 and Day -2. Patients will be admitted the day prior to receiving the study drug (Day -1) and will remain in the CRU under clinical supervision for at least 48 hours after the last dose is received on Day 7. Patients will be discharged on Day 9, but return to the CRU 7 days after their last dose of study drug for follow-up evaluations. The study personnel will telephone each patient 14 days after the last dose of study drug and conduct a Follow-Up interview to assess the patient's condition.

The patient's eligibility assessment will be reviewed by an external medical team based on key protocol inclusion and exclusion criteria to promote appropriate patient enrollment and data quality. Sites should submit specific Screening information (detailed in the Massachusetts Clinical Trials Network and Institute [MGH CTNI] manual) within 72 hours after the Screening

[figure not shown]
Visit for review by the external medical team prior to proceeding to Check-in. Subjects who are deemed eligible by the Principal Investigator and confirmed by the Medical Monitor will undergo the SAFER Interview³⁰ by clinicians at the MGH CTNI. To ensure that appropriate subjects are entered into the study, a remote interview will be conducted by MGH CTNI raters. The assessments administered will be the SAFER Interview, which will include the HAM-D17, and the MGH ATRQ. The interview will be performed remotely by the MGH CTNI rater, and the subject will be contacted at his or her home or other off-site location after the Screening Visit, during which call the above assessments will be performed. Sites will be notified of the results within 24 hours of the interview. Only subjects whose eligibility will be confirmed by the SAFER Interview will be allowed to proceed in the study.

The study design is summarized in [Figure 2](#). Study assessments will be performed at the visits and time points outlined in the Time and Events Schedule ([Table 1](#)).

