Approximately 60 qualified patients will be randomized to study drug in a 1:1:1 ratio. Arm 1 will consist of approximately 20 patients who will receive REL-1017 25 mg. Arm 2 will consist of approximately 20 patients who will receive REL-1017 50 mg. Arm 3 will consist of approximately 20 patients who will receive Placebo. REL-1017 will be provided as a powder and prepared as a solution with Ocean Spray[®] Diet Cranberry Juice on site to obtain a final volume of 100 mL for dosing. The study drugs will consist of the following:

- Arm 1: REL-1017 (d-methadone) 75 mg of powder in 100 mL of Ocean Spray[®] Diet Cranberry Juice QD on Day 1, 25 mg of powder in 100 mL Ocean Spray[®] Diet Cranberry Juice QD on Day 2-7.
- Arm 2: REL-1017 (d-methadone) 100 mg of powder in 100 mL of Ocean Spray[®] Diet Cranberry Juice QD on Day 1, 50 mg of powder in 100 mL Ocean Spray[®] Diet Cranberry Juice QD on Day 2-7.
- Arm 3: Placebo = 100 mL Ocean Spray[®] Diet Cranberry Juice.

Figure 2: Flow Chart of Study Design

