5.4 Selection of Doses

Since extensive clinical experience is available for racemic methadone and some clinical experience for d-methadone,^{31,32,33} the 25 mg and 50 mg doses are selected based on the comparative characteristics of racemic methadone and available data with d-methadone in healthy patients.

The following rationale was applied. In recent studies in healthy patients, an oral dose of at least 0.2 g/kg (10 mg to 20 mg) or 8 mg to 15 mg was well tolerated and provided information on the PK of individual isomers and the interaction with other CYP3A4 substrate drugs.³⁴ Moreover, in the study of REL-1017 alone in opiate-naive patients, a dose as high as 150 mg was tested with no severe adverse reactions. Due to differences in the pharmacologic activity of the methadone enantiomers, the same incidence and severity of opioid-related AEs observed with racemic methadone are not anticipated to occur with the administration of d-methadone.

Based on the safety data from Protocol REL-1017-111, single doses of 5 mg, 20 mg, 60 mg, 100 mg, and 150 mg of REL-1017 or Placebo were well tolerated. The results of Protocol REL-1017-112 evaluated 10 days of dosing with as high as 75 mg, and no impact on safety was observed. Regardless of the confirmed dose proportionality, the comparison of concentration and exposure between the 50 mg and 75 mg REL-1017 treatment groups demonstrated only slight differences. Consequently, 25 mg and 50 mg doses were chosen for administration in Protocol REL-1017-202 as daily doses over a period of 7 days.

To reach steady state more quickly for REL-1017 25 mg and REL-1017 75 mg dosing arms, a loading dose on Day 1 was added to each dosing arm, REL-1017 75 mg on Day 1 followed by 25 mg REL-1017 on Day 2-7; 100 mg REL-1017 on Day 1 followed by 50 mg REL-1017 on Day 2-7.

PK/PD modelling, based on the demonstrated AUC_{τ} of d-methadone in pre-clinical and clinical studies and on the AUC_{τ} of ketamine at doses that provide antidepressant efficacy, supports the conclusion that d-methadone 25 mg and 50 mg QD are the predicted efficacious doses.

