6.1.4 Dosing Period (Day 1 to Day 7)

The dosing period will begin on Day 1 and continue through the last dose of study drug on Day 7 (End of the Dosing Period [EDP]). Study drug will be administered in the morning. Assessments during the dosing period will include measures of safety and tolerability, PK, and efficacy. For patients who discontinue study drug prior to Day 7, all EDP assessments should be completed according to the Time and Events Schedule (Table 1) provided informed consent has not been withdrawn.

6.1.5 24-Hour Post-Dose Assessments (Day 8)

On Day 8, patients will be evaluated 24 hours after the final dose of study drug on Day 7 according to the Time and Events Schedule (Table 1). Blood samples will also be drawn for PK analysis approximately 24 hours after the last dose of study drug.

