6.3 Pharmacokinetic Assessments

Venous blood samples will be collected daily from Day 1 through Day 7, Day 8, Day 9, and on Day 14 at the following time points to determine the plasma concentrations of REL-1017:

- PK sampling will be done on Day 1 at 1 hour pre-dose and 0.5, 1, 2, 4, 6, 8, and 12 hours post-dose.
- On Day 2 through Day 7, sampling will be done 1 hour pre-dose.
- On Day 8, sampling will be done approximately 24 hours after the last dose of study drug (on Day 7).
- On Day 9, sampling will be done approximately 48 hours after the last dose (on Day 7).
- On Day 14, sampling will be done approximately 168 hours after the last dose (on Day 7 ± 3 days).

A safety catheter will be placed before dosing on Day 1 until the 12-hour post-dose sample has been collected in the event a rescue medication is required.

Samples will be collected, processed, and shipped according to the site's SOPs and instructions from the Sponsor or the bioanalytical laboratory. The blood volumes required for PK sampling are available in Appendix 11.1.

The plasma samples will be analyzed by the bioanalytical laboratory using validated methods.

Plasma samples will be shipped frozen on dry ice from the research site to the bioanalytical laboratory. Samples will not be shipped without prior arrangement with the bioanalytical laboratory and notification of the Sponsor.

Drug concentration information that may unblind the study will not be reported to the study site or blinded personnel until the study has been unblinded.

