8.1.5 Demographics and Other Baseline Characteristics

Demographics and Baseline characteristics (age, sex, race, ethnicity, body weight, height, oral body temperature, and BMI) will be summarized using descriptive statistics (number of patients, mean, SD, median, minimum, and maximum for continuous variables and the proportion of patients for categorical variables) for the Safety population. No formal statistical comparison between the groups will be performed. Demographics and height will be recorded at Screening only. Weight and oral body temperature will also be recorded at Check-in (Day -1), EDP (Day 7), and EOP (Day 14). In addition, BMI will be calculated at Screening.

The patient's eligibility for participation in the study will be determined with the inclusion and exclusion criteria at Screening. The inclusion and exclusion criteria will be reviewed again at Check-in (Day -1) when the patient is admitted to the CRU. The study restrictions review will also occur at Check-in (Day -1).

Patients will be confined to the CRU from Check-in (Day -1) through Discharge on Day 9. Patients will be administered study drug daily from Day 1 through Day 7.

Randomization will occur on Day 1 prior to administration of the first dose of study drug. The treatment assignment for each patient will be assigned through the IWRS in a 1:1:1 ratio (REL-1017 25 mg, REL-1017 50 mg, or Placebo), and the randomization schedule will be stratified based on patients receiving concomitant ADTs that are cytochrome (CYP) 2B6 inhibitors (e.g., paroxetine, fluoxetine) versus those who are not.

Medical history and psychiatric history will be coded into the most recent version of MedDRA available (Version 16.0 or higher). Medical history will be listed by treatment arm and patient at

Screening and Check-in (Day -1). Psychiatric history will be listed by treatment arm and patient at Screening only.

Prior and concomitant medications will be assigned a 12-digit code using the most recent version of the WHO drug codes available. Prior and concomitant medications will be listed by treatment arm and patient. Medication history (prior medications) will be listed at Screening, and concomitant medications will be listed at every visit from Check-in (Day -1) through EOP (Day 21) and summarized by treatment.

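### Section 5.1 lists doses for Day 1 and Days 2 to 6 only, while the rest of the protocol places a dose on Day 7 from which end-of-treatment measures are timed

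*Combined protocol and SAP*

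**What the plan says.** Seven places in the current protocol put a dose on Day 7:

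- Synopsis, dose schedule: "REL-1017 75 mg QD Day 1, 25 mg REL-1017 QD Day 2-7" for Arm 1 and "REL-1017 100 mg QD Day 1, 50 mg REL-1017 QD Day 2-7" for Arm 2.
- Table 1: the study drug dosing row is marked on every day from Day 1 to Day 7.
- Section 3.2: patients receive "daily doses of REL-1017 or Placebo for 7 consecutive days", and the description of each active arm ends its maintenance dose with "Diet Cranberry Juice QD on Day 2-7".
- Section 5.4: "25 mg REL-1017 on Day 2-7" for the lower-dose arm, and the same days for the other active arm.
- Section 6.1.4: the dosing period is to "continue through the last dose of study drug on Day 7".
- Section 6.3: "On Day 8, sampling will be done approximately 24 hours after the last dose of study drug (on Day 7").
- Section 8.1.5: "Patients will be administered study drug daily from Day 1 through Day 7".

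Section 5.1, Study Drug Administration, differs. It sets out what each of the three arms receives under two headings, one for Day 1 and one for Days 2 to 6. No Day 7 entry follows for either active arm or for placebo. The section does not say that dosing ends on Day 6, and it gives no count of doses.

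**The concern.** Section 5.1 is the section titled for study drug administration, so pharmacy and site staff can be expected to consult it. Read by itself, it leaves Day 7 without a stated dose.

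Much of the end-of-treatment schedule depends on that dose:

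- **Efficacy:** the Day 7 MADRS, SDQ, CGI-S and CGI-I are post-dose ratings taken within 3 h of dosing (Table 1 footnote k; Sections 6.4.1 and 6.4.2.2).
- **Safety:** the Day 7 ECG (Section 6.2.4), CADSS (6.2.6.1) and PSRS (6.2.6.4) are set at 2 h post-dose. Safety is the primary objective.
- **PK:** the Day 7 sample is 1 h pre-dose, and the Day 8, 9 and 14 samples are about 24, 48 and 168 h after the Day 7 dose (Sections 6.3 and 8.1.4.4).

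If no dose were given on Day 7, the post-dose measures would have no dose that day to be timed from. PK samples reported at nominal times would also carry the wrong time since dosing: a Day 8 concentration labelled 24 h would in fact be a 48 h value.

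**Working it through.** This is counting and arithmetic. No power or sample-size formula is involved, and the protocol gives none.

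**Inputs**

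- Arm 1: 75 mg on Day 1, then 25 mg per maintenance day. Arm 2: 100 mg on Day 1, then 50 mg per maintenance day (Synopsis; Sections 3.2 and 5.1).
- Last dosing day: Day 7 in the seven places listed; Day 6 if Section 5.1 is taken literally.
- Participation: 30 days of screening, 7 of treatment and 14 of observation and follow-up, up to 51 days in all (Synopsis; Section 4.1).

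**Formulas**

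- Doses = 1 + number of maintenance days.
- Cumulative dose = Day 1 dose + maintenance dose × number of maintenance days.
- Hours after last dose = (sampling day − last dosing day) × 24.

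**The protocol's own figures, last dose on Day 7**

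- Doses: 1 + 6 = 7, matching Section 3.2.
- Participation: 30 + 7 + 14 = 51 days, matching the Synopsis.
- PK times: (8 − 7) × 24 = 24 h; (9 − 7) × 24 = 48 h; (14 − 7) × 24 = 168 h, matching Section 6.3.
- Cumulative dose: 75 + 6 × 25 = 225 mg in Arm 1; 100 + 6 × 50 = 400 mg in Arm 2.

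**Section 5.1 taken literally, last dose on Day 6**

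- Doses: 1 + 5 = 6.
- Cumulative dose: 75 + 5 × 25 = 200 mg in Arm 1; 100 + 5 × 50 = 350 mg in Arm 2.
- PK times, with visits kept on their calendar days: (8 − 6) × 24 = 48 h; (9 − 6) × 24 = 72 h; (14 − 6) × 24 = 192 h.

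| Quantity | Last dose Day 7 | Section 5.1 literal | Difference |
|---|---|---|---|
| Doses | 7 | 6 | −1 |
| Cumulative dose, Arm 1 | 225 mg | 200 mg | −25/225 = −11.1% |
| Cumulative dose, Arm 2 | 400 mg | 350 mg | −50/400 = −12.5% |
| Day 8 PK | 24 h | 48 h | +24 h |
| Day 9 PK | 48 h | 72 h | +24 h |
| Day 14 PK | 168 h | 192 h | +24 h |

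Two details limit the reach of the table. First, the Day 7 PK sample is pre-dose. It falls about 24 − 1 = 23 h after the Day 6 dose under either reading, so only its label depends on a Day 7 dose. Second, the Day 14 sample has a window of ±3 days, which is wider than the 24 h shift. The Day 8 and Day 9 samples have no such window; their times are stated only as approximate.

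For the Day 7 ratings, if the clock time is kept, 0 to 3 h after a Day 7 dose becomes about 24 to 27 h after a Day 6 dose.

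**The case against.** The strongest reply is that this is a slip in one heading which nobody would act on. In the current text only Section 5.1 omits Day 7, and the study title itself describes 7-day dosing. A site working from Section 5.1 alone would still meet the Day 7 mark in the dosing row of Table 1. It would also meet Day 7 assessments labelled post-dose, which would expose the gap. Section 5.2.3 leaves preparation and administration details to a pharmacy manual that is not among the documents and may already be consistent.

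Much of this stands, and it limits what can be claimed. A reader might infer several stronger things that the documents do not support:

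- **That the protocol prescribes a six-dose course.** It does not. Section 5.1 omits Day 7; it neither states six doses nor says to withhold one on Day 7.
- **That Section 5.1 overrides the other passages.** The protocol does not rank its sections. Sections 3.2 and 5.4 also give doses by arm and day.
- **That the Day 14 visit, the follow-up contact and the inpatient stay are disturbed.** Sections 6.1.6 to 6.1.8 tie these to the last dose and expressly cover patients who stop before Day 7. The Day 14 and follow-up visits also have ±3-day windows.
- **That regimens were mixed within an arm across the roughly 10 sites.** Nothing in the documents shows that any patient was dosed from Section 5.1 alone.

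What the reply does not remove is the contradiction. A majority of passages is not a dosing instruction, and an unseen manual cannot be assumed to settle the matter. Nor is the problem confined to the amendment tables: the wording is in the current body of Section 5.1.

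**Conclusion.** The inconsistency is real and needs correcting. Section 5.1 gives no Day 7 dose for any arm, while seven other places put a dose on that day and the end-of-treatment efficacy, safety and PK times are set from it.

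Its size is conditional. The reductions of 25 mg (11.1%) in Arm 1 and 50 mg (12.5%) in Arm 2, and the 24 h shift in the Day 8, 9 and 14 PK times, arise only if a site follows Section 5.1 literally. The PK shift further assumes that visits stay on their calendar days. If every patient is dosed on Day 7, none of these differences occurs.

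This is a drafting inconsistency, not a flaw in the chosen design. The analysis populations, the mixed model and the sample size do not depend on how it is resolved. Nothing here says which course is right; that is for the sponsor to state.

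**What to change.** The sponsor should state the intended course and reconcile Section 5.1 with the Synopsis, Table 1 and Sections 3.2, 5.4, 6.1.4, 6.3 and 8.1.5, so that each dosing day has one stated dose per arm. The pharmacy manual should be checked against the reconciled text.

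If any patient was dosed from Section 5.1 as it stands, the report should give the actual number of doses per patient, and PK sampling and rating times should be computed from actual dose times instead of nominal ones.

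The cost is a short text correction and a check of the manual, with no added patients, visits or procedures.

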CADSS	Clinician Administered Dissociative States Scale
CGI	Clinical Global Impressions
CGI-S	Clinical Global Impressions of Severity
CGI-I	Clinical Global Impressions of Improvement
CGS-19755	Selfotel, NMDA Receptor Antagonist
CL/F	Apparent Clearance/Bioavailable Fraction Absorbed
C _{max}	Maximum Observed Plasma Concentration
C _{min}	Minimum Observed Plasma Concentration
CNS	Central Nervous System
COWS	Clinical Opiate Withdrawal Scale
CRU	Clinical Research Unit
C _{ss}	Concentration at Steady State
C-SSRS	Columbia-Suicide Severity Rating Scale
C _{ss} /F	Steady State Clearance
CTNI	Clinical Trials Network and Institute
CV	Coefficient of Variation
CYP	Cytochrome
DNA	Deoxyribonucleic Acid

DSM-5	Diagnostic and Statistical Manual, Fifth Edition
ECG	Electrocardiogram
eCRF	Electronic Case Report Form
ECT	Electroconvulsive Therapy
EDC	Electronic Data Capture
EDP	End of the Dosing Period (Day 7)
EDTA	Ethylene Diamine Tetra-acetic Acid
EOP	End of the Observation Period (Day 14)
EW	Early Withdrawal
FDA	United States Food and Drug Administration
FU	Follow-up
GCP	Good Clinical Practice
GGT	Gamma-Glutamyl Transferase
GluR1	Glutamate Receptor 1
HAM-D-17	Hamilton Depression Rating Scale
HCl	Hydrochloride
hERG	Human Ether-A-Go-Go-Related Gene
HIV	Human Immunodeficiency Virus
HR	Heart Rate
IC ₅₀	Half Maximal Inhibitory Concentration
ICF	Informed Consent Form
ICH	International Council for Harmonisation of Technical Requirements for Pharmaceuticals for Human Use
ID	Identification
IK _r	Delayed Rectifier Current Channel
IRB	Institutional Review Board
IV	Intravenous
IWRS	Interactive Web Response System
K _i	Thermodynamic Inhibition Constant
λ _z	Apparent Termination Elimination Rate Constant
LD ₅₀	Half Maximum Lethal Dose
LS	Least Square Means
MAD	Multiple Ascending Dose
MADRS	Montgomery-Asberg Depression Rating Scale
MAOI	Monoamine Oxidase Inhibitor
MDD	Major Depressive Disorder
MDE	Major Depressive Episode
MedDRA	Medical Dictionary for Regulatory Activities (Version 16.0 or Higher)
MGH	Massachusetts General Hospital
mGlu2/3	Metabotropic Glutamate (mGlu) Receptors

MINI	Mini International Neuropsychiatric Interview, Version 7.0.2
MK-801	Dizocilpine, NMDA Receptor Antagonist
MTD	Maximum Tolerated Dose
mTORC1	Rapamycin Complex 1
NMDA	N-methyl-D-aspartate
PD	Pharmacodynamic(s)
PFC	Prefrontal Cortex
PK	Pharmacokinetic(s)
PSD95	Postsynaptic Density Protein 95
QD	Quaque Die (Once Daily)
QT	Measure of the Time between the Start of the Q Wave and the End of the T Wave in the Heart's Electrical Cycle
QTc	Corrected QT
QTcF	QT Interval with Fridericia's Correction
RBC	Red Blood Cell (Count)
REL-1017	d-Methadone (Dextromethadone) Hydrochloride
Relmada	Relmada Therapeutics, Inc.
RR	Respiratory Rate
rTMS	Repetitive Transcranial Magnetic Stimulation
SAD	Single Ascending Dose
SAE	Serious Adverse Event
SAFER	S tate versus T rait; A ssessability; F ace Validity; E cological Validity; and R ule of Three Ps (Pervasive, Persistent, and Pathological)
SAP	Statistical Analysis Plan
SD	Standard Deviation
SDQ	Symptoms of Depression Questionnaire
SIGH-D	Structured Interview Guide for the HAM-D-17
SIGMA	Structured Interview Guide for the MADRS
SMS	Scheduled Measurement System
SNRI	Serotonin and Norepinephrine Reuptake Inhibitor
SOP	Standard Operating Procedure
SSRI	Selective Serotonin Reuptake Inhibitor
Syneos Health	Syneos Health, Inc. (formerly INC Research, Inc. [Contract Research Organization])
t _{1/2}	Apparent Terminal Elimination Half-Life
T3	Triiodothyronine
T4	Thyroxine
T _{max}	Time to Maximum Observed Plasma Concentration
TSH	Thyroid Stimulating Hormone
ULN	Upper Limit of Normal

VAS	Visual Analogue Scale
VNS	Vagus Nerve Stimulation
V _{ss} /F	Volume of Distribution at Steady State
WBC	White Blood Cell (Count)
WHO	World Health Organization

